1.3.2.1 Intra-operative CT-guided Endoscopic Surgery for ICH (ICES)

The ICES technique involves the stereotactic placement of an endoscopic sheath into the hematoma. The hematoma is then evacuated using suction and irrigation from two pre-specified depths. The endoscope is then used to make an assessment of the volume of residual hemorrhage as well as to assess, and potentially control, any active intracranial hemorrhage using cautery.⁵³ In a small, single-center series of six patients, the operators were able to achieve an 80% reduction in hemorrhage volume and a 60% reduction in midline shift. In a second small, single-center trial, ten patients were randomized between the ICES technique and medical management. In the ICES group (n = 6), the operators achieved an 80% reduction in hematoma volume, while the medical management group demonstrated an 80% enlargement, both over a 24-hour period after treatment allocation.⁵⁴ The trial was ultimately halted due to slow enrollment and the recognition from the operators that the technique required optimization within the context of a single-arm study prior to the performance of a randomized trial. Recently, a larger trial by Vespa et al⁵⁵ randomized 14 patients to receive ICES and 4 to receive medical management. The control arm of the

MISTIE trial was also used to analyze the trial outcome. Results demonstrated a 71.2% reduction in ICH immediately post treatment; at 72 hours, the reduction in ICH volume was significant (21.1 cm^3 , $p = 0.0002$) in the ICES group as compared to the medical group. Despite being underpowered to yield significant clinical outcome, there was a trend towards good neurological outcome ($\text{mRS} \leq 3$) for the ICES cohort (42.9% vs. 23.7%, $p = 0.19$). Notably, the trial demonstrated the feasibility of ICES as a safe and effective modality with a potential to yield good clinical outcome.⁵⁵

The MISTIE II trial evaluated safety and efficacy of hematoma evacuation after ICH using minimally invasive surgery and rt-PA in ICH evacuation in 2 stages (dose finding occurred in 2005-2009 and safety analysis during 2009-2012).⁷² There were seventy-nine surgical subjects and 39 medical subjects with minimally invasive surgery and rt-PA in ICH evacuation for mean hematoma volume; 69 subjects in the surgery cohort underwent surgical aspiration and rt-PA and 10 subjects underwent surgical aspiration alone. The reduction in edema was 5.6 in the surgical arm and -11.4 in the medical arm ($P < 0.001$) and the authors concluded that the finding was consistent with the hypothesis that hematoma evacuation would lead to a significant reduction in edema volume.

The MISTIE III Trial was a randomized, blinded endpoint, open label, phase III study that was conducted in the U.S., Canada, Europe, Asia, and Australia (Hanley, 2019)⁷⁰. There were 78 hospitals that enrolled and treated 499 patients with an intracerebral hemorrhage ($n=250$ MISTIE arm and $n=249$ standard medical arm). The MISTIE arm subjects were treated with image-guided minimally invasive catheter evacuation followed by thrombolysis.

The main objective was to assess if minimally invasive surgery (MIS) followed by thrombolytic irrigation of the catheterized intracerebral hemorrhagic clot was safe and could improve functional outcomes at 365 days after a stroke. The primary efficacy outcome was good functional outcome (mRS score 0-3) at 365 days after a stroke and the safety outcomes were all-cause mortality at 30 days, procedure related mortality at 7 days, bacterial brain infection at 30 days, and symptomatic bleeding within 72 hours from last dose. The trial used an imaging core lab and a Data Safety Monitoring Board (DSMB) reviewed clinical safety data.

The trial arms were well matched, but there was a higher number of subjects actively taking anticoagulants at the time of enrollment in the MISTIE arm (10%) compared to the SOC arm (4%). For the primary outcome of the mITT set after adjusting for baseline variables, 45% of subjects ($n=249$) in the MISTIE arm achieved an mRS score of 0-3 at 365 days compared to 41% in the SOC arm ($n=240$). The MISTIE arm had fewer subjects that

died within 7 days compared to the SOC arm (1% vs 4%, P=0.018, respectively) and also at 30 days (9% vs 15%, P=0.066), respectively. There were 2 bacterial brain infections with 30 days in the MISTIE arm and none in the SOC arm. The MISTIE arm and SOC arm had comparable symptomatic brain bleeds with 72 hours from the last thrombolytic dose (2% vs 1%, P=0.325). However, asymptomatic brain bleeds within 72 hours from the last thrombolytic dose was significantly higher in the MISTIE arm. There were fewer serious adverse events reported in the MISTIE arm compared to the SOC arm (126 events vs 142, P=0.012), which was statistically significant. The authors reported that an exploratory analysis of clot removal did show an association between extent of removal and a lower mRS score (0-3), possibly due to the benefit of the procedure or due to unmeasured confounding effects. Furthermore, the authors concluded that there were few negative consequences to MISTIE, and it was safe with regards to serious bleeding and infection. The procedural risks were also reported as comparable between the two arms.

Another analysis of the MISTIE III data was published (Awad et al.2019) to examine results of a multivariate and univariate model to assess hematoma evacuation efficacy in relation to mRS scores of 0-3.⁷¹ Using a linear spline model, the authors determined that a reduction of ICH hematoma volume of ≤ 15 mL correlated with a good functional outcome of mRS 0-3 (OR 0.90, 95% CI 0.85-0.96, p= 0.002). The results indicated that a reduction beyond the 15 mL threshold increased the chance of having a good outcome by 10% per mL of hematoma removed. The reduction of hematoma volume by $\geq 70\%$ increased the likelihood to achieve an mRS 0-3 score; each additional mL removed beyond 70% translated to a 6% improvement to achieve a good outcome for mRS 0-3 (OR 1.06, 95% CI 1.02-1.10, p=0.002). End of treatment ICH volume < 30 mL also had a significant better survival outcome (OR 5.545, CI 2.362-13.019, p<0.001). At ≤ 30 mL end of treatment ICH volume, or $>53\%$ volume reduction, a mortality benefit was observed. Initial hematoma volume, history of hypertension, irregular-shaped hematoma, number of alteplase doses given, surgical protocol deviations, and catheter manipulation problems were significant factors in failing to achieve ≤ 15 mL goal evacuation. The analysis was significant, as it was the first report of thresholds for reduction of ICH volume correlated with mortality and functional outcomes.

1.4 Conclusions

Intracranial hemorrhage is a devastating disease associated with poor clinical outcomes. To date, no surgical or medical therapy has been demonstrated to improve outcomes in these patients. Of all the strategies tested, the most encouraging data exist for minimally invasive strategies employed to achieve a reduction in hemorrhage volume. Initial data derived from preliminary studies of thrombolytic-assisted catheter drainage have been encouraging, but there are

significant potential shortcomings of this technique compared to the purely mechanical approach with the Artemis Neuro Evacuation Device (Artemis Device). Early experience with the Apollo/Artemis in regards to its application to remove parenchymal hemorrhages has evolved. As such, now that the technical approach has matured, it is necessary to proceed with a pivotal randomized controlled trial to assess the potential for clinical benefit and safety of MIS with the Artemis Device in patients with supratentorial ICH.

2. The Artemis Neuro Evacuation Device

A successor to the Apollo System, the Artemis Device is a surgical instrument designed to aid a physician in the removal of tissue and/or fluid during image-guided neurosurgery. The Artemis Device has two functions. These functions are control and transfer of aspiration and generation of rotational energy. Aspiration is generated by a Penumbra Aspiration Pump, which the Artemis Device connects to through flexible tubing. The Artemis Device has a rigid cannula containing a wire to facilitate removing tissue and/or fluid with the assistance of rotational energy and aspiration. The Artemis cannula fits through the working channels of commercially available neuroendoscopes (e.g. Lotta, Karl Storz, Tuttlingen, Germany) such that clot evacuation can be performed under direct visualization.⁵⁶ The technique is very similar to the ICES technique in that a sheath is placed within the hematoma and evacuation is typically performed under direct endoscopic visualization. In some settings, periodic evaluation of the remaining hematoma is performed using intra-procedural CT or ultrasound.⁵⁶ The method of action of removal is first vacuum aspiration, which draws the tissue and/or fluid into the lumen of the Artemis cannula. Next, the wire inside the lumen of the Artemis cannula is rotated, facilitating movement of any tissue and/or fluid that may otherwise clog the cannula lumen.

The conceptual principles of operation remain the same for the Artemis Neuro Evacuation Device and the Apollo System, both of which are used for the controlled aspiration of tissue and/or fluid removal.

The Artemis Device utilizes rotational energy, rather than vibrational energy used for the Apollo System, to prevent clogging of tissue and/or fluid aspirated into the Artemis cannula. The helical wire prevents the Artemis cannula from clogging by interacting with the aspirated tissue and/or fluid throughout the entire length of the cannula. The electrical power to rotate the wire in the Artemis cannula is provided by a battery which drives a motor, both of which are contained in the disposable handle.

[figure not shown]
In an initial multi-center, retrospective series of 29 ICH patients undergoing treatment with the Apollo System, an average reduction in hemorrhage volume of 54% was achieved, with a reduction of the hemorrhage volume to < 10 cm³ in 48% of subjects treated. As opposed to the ICES technique, in most cases, no drainage catheters were placed following the initial evacuation.⁵⁶

Thus, the Artemis Device potentially provides a means by which to efficiently and reliably achieve a minimally invasive, mechanical evacuation of intracranial hemorrhage under

direct visualization and control using a neuroendoscope without the requirement for subsequent catheter placement and thrombolytic irrigation.

The Apollo System received FDA clearance for the controlled aspiration of tissue and/or fluid during surgery of the ventricular system or cerebrum in March 17, 2016 and CE marking in May 10, 2016 and is commercially available in the United States and throughout Europe. The Artemis Neuro Evacuation Device received FDA clearance (K171332) on August 14, 2017.

Figure 1: Image of the Artemis Neuro Evacuation Device cannula at Site of Bleed

3. Risk Analysis

The overall risks associated with the procedure depend on a number of factors including, but not limited to, the device, anesthesia, disease condition and medical management. The primary risks to subjects in this study are associated with the minimally invasive surgical (MIS) procedure and the associated general anesthetic. Imaging performed throughout the course of the study, while specified in the protocol, falls within the standard of care for the initial evaluation and follow-up of patients with intracranial hemorrhage. The MIS procedure is performed in a manner which is similar to that of other neuroendoscopic procedures and the associated risks are similar. In brief (see Section 6.7 for a detailed description of the procedure), the MIS procedure involves the creation of a burr hole/1 – 2 cm craniectomy and dural incision. An endoscopic sheath is then placed through the access site into the hematoma under imaging control using neuronavigation. Under endoscopic guidance, the hemorrhage is evacuated using the Artemis Device. Following the evacuation, the endoscope and Artemis Device are removed. Intraoperative CT imaging is performed to assess the remaining hemorrhage volume and to assess for immediate procedural complications. Ultrasound may also be used during the procedure to evaluate removal of the hematoma. Based on the intra-operative CT imaging, either an additional pass(es) is made or the procedure is terminated. Following the procedure, all equipment is removed and the cranial access is closed in a standard manner.

The potential clinical risks that may be associated with the use of Artemis Device or with the procedure include, but may not be limited to:

Hematoma expansion	Increased blood pressure
Fever	Infections
Headaches	Seizures
Vomiting	Intraventricular hemorrhage
Hyperglycemia	Hydrocephalus
Edema	Thromboembolic events
Re-bleeding	Decreased consciousness
Death	Craniotomy
Bleeding	Unintended Removal of Tissue leading to Neurological and/or sensory deficit

The complications particularly related to the procedure include bleeding, infection, or damage to surrounding structures during the creation of the cranial access or placement of the sheath. During evacuation of the hemorrhage with the Artemis Device, there is the possibility of inducing or encountering an additional hemorrhage in the operative bed. In a retrospective multicenter study of the Apollo procedure for the treatment of ICH, re-bleeding was encountered in 2 of 29 subjects (6.9%).⁵⁶ There may be residual fluid or blood requiring additional surgery in the future.

The risk related to the general anesthetic in this patient population is estimated to be approximately 1 – 5% for major morbidity and mortality (e.g. airway management issues, aspiration, hypotension or drug reaction), given that their American Stroke Association score would typically be 4 or 4e in this category of patients.^{57,58} A thorough risk analysis was performed as part of design control recommendations of the Quality System Regulation (21 CFR 820).

Best medical management (MM) will be provided as specified in the AHA/ESO guidelines.^{18,59} As such, for subjects randomized to the MM arm of the study, there is no additional risk. With the natural history of ICH/IVH and standard of care, there are expected medical events, or expected adverse experiences, that are listed below. Since these medical events are expected in the disease process or after MM, the events are thus expected to occur in any patients with the disease irrespective of the treatment arm. Best medical management (MM) will be provided as specified in the AHA/ESO guidelines.^{19,60} As such, for subjects randomized to the MM only arm of the study, there is no additional risk.

EXPECTED EVENTS	
Nervous System	Other Systems
Cerebral Edema and Mass Effect	Acute Kidney Injury
Brain Stem Compression	Acute Respiratory Distress Syndrome
Brain Herniation	Aspiration
Brain Re-bleeding near Initial Hemorrhage Site	Catheter-related vascular infections
Catheter Tract Bleeding/Hemorrhage Enlargement	Deep Vein Thrombosis
Cerebral Infarction	Dysphagia
Cerebritis	Fever/Hyperthermia

Coma	Hyponatremia
Death	Hypoxia
Decreased Level of Consciousness	Hypercapnia
Delirium	Hyperglycemia/Hypoglycemia
Diaschisis	Hypertension (Induced or Not Induced)
Elevated ICP	Hypotension (Induced or Not Induced)
Headache	Impaired Nutritional Status
Hydrocephalus	Infectious Complications
Intracranial Abscess	Nausea
Meningitis (Bacterial or Non-Bacterial)	Vomiting
Perihematomal Ischemia	Pericarditis
Seizures	Pulmonary Edema
Ventriculitis (Bacterial or Non-Bacterial)	Pneumonia (including Ventilator-Associated)
	Pulmonary Embolus
	Sepsis/Bacteremia
	Spontaneous Bleeding from Non-Cerebral Sites
	Thromboembolic Complications
	Urinary Tract Infections
	Vascular Injury/Puncture Site Bleeding

Medical Management of ICH should include¹⁸:

- **Hemostasis and Coagulopathy, Antiplatelet Agents, and Thromboembolic Prophylaxis:** Patients with ICH should have intermittent pneumatic compression for prevention of venous thromboembolism beginning the day of hospital admission.
- **Blood Pressure Management:** Early BP reduction with an SBP target of 140 mmHg for patients with ICH presenting with an SBP between 150 and 220 mmHg and without any contraindication to acute BP treatment. For patients with ICH presenting with an SBP > 220 mmHg, aggressive BP reduction with continuous intravenous infusion and frequent BP monitoring may be reasonable.
- **General Monitoring and Nursing Care:** Initial monitoring and management of patients with ICH should take place in an intensive care unit or dedicated stroke unit with physician and nursing neuroscience acute care expertise.
- **Glucose Management:** Glucose should be monitored. Both hyperglycemia and hypoglycemia should be avoided.
- **Seizures and Antiseizure Drugs:** Clinical seizures should be treated with antiseizure drugs. Patients with a change in mental status who are found to have electrographic seizures on electroencephalography should be treated with antiseizure drugs.
- **Management of Medical Complications:** A formal screening procedure for dysphagia should be performed in all patients before the initiation of oral intake to reduce the risk for pneumonia.

- **Prevention of Recurrent ICH:** BP should be controlled in all patients with ICH. Measures to control BP should begin immediately after ICH onset.
- **Rehabilitation and Recovery:** Given the potentially serious nature and complex pattern of evolving disability and the increasing evidence for efficacy, it is recommended that all patients with ICH have access to multidisciplinary rehabilitation.

In order to minimize risks to subjects enrolled into the clinical study, Investigators will be qualified in accordance with FDA requirements and Good Clinical Practice. Investigators using the devices will be trained on proper use of the Artemis Device in accordance with Section 8.1 herein prior to initiation of treatment at each facility. Patients will be carefully evaluated before treatment to ensure that the treatment with the Artemis Device is appropriate. During treatment, the procedure should be performed in an operating room (OR) or a procedure room with appropriate resources for emergent intervention should complications arise. All treating facilities should conform to national guidelines, and the treating physician should be experienced in treating patients presenting with this condition.

Subjects will be carefully monitored during the procedure and the follow-up period. Clinical study participants will be routinely questioned to confirm whether adverse events/effects have occurred at study visits. The physician should examine and perform various diagnostic tests before, during, and after the procedure with appropriate long-term follow-up.

The anticipated risks will be monitored during the study for changes in event rates. On-going monitoring of adverse events, serious adverse events, and device malfunctions will be conducted during the study. A Clinical Events Committee (CEC) will adjudicate pre-defined AE/SAEs for causality and attribution. A Data Safety Monitoring Board (DSMB) will monitor the overall safety during the clinical study. Penumbra, Inc. or its representatives will continue to monitor the complaints and report them as mandated by FDA or other national agencies.

4. Study Overview

The primary aim of minimally invasive surgery (MIS) for supratentorial intracranial hemorrhage is to achieve an atraumatic evacuation of blood products from the brain to prevent the secondary injury that occurs after the initial bleed. To date, several pilot studies and a small Phase II feasibility trial have suggested that MIS with catheter mediated thrombolytic irrigation may be associated with an improvement in clinical outcomes in ICH.^{44,48,50,54,60-62} Currently no prospective study exists to evaluate the efficacy of MIS with the Artemis Device for this purpose. The purpose of this pivotal randomized study is to demonstrate the efficacy of MIS with the Artemis Device to improve outcomes in patients with small to moderate volume supratentorial ICH.

4.1 Study Design

This is a prospective, multicenter randomized study comparing MIS with MM (MIS group) with MM alone in patients with supratentorial intracerebral hemorrhages.

MM will be determined by practice standards utilized in the operator's region of practice and following the existing AHA/ESO guidelines (as above). Patients will be enrolled who meet the inclusion and exclusion criteria, with consent to participate, and are randomized to either MIS or MM. Subjects will be randomly assigned by a central web-based system in a 2:1 manner to treatment with MIS or MM. Data for each subject will be collected at the time of enrollment and treatment, and at subsequent follow-up visits.

4.2 Study Objectives/Endpoints

4.2.1 Primary Endpoints

The primary objective is to demonstrate the efficacy of MIS in patients with supratentorial intracranial hemorrhage to improve clinical outcomes when compared with best medical therapy with respect to the endpoints defined as:

- Efficacy Endpoint: 180 day global disability assessed via the ordinal modified Rankin score (mRS)
- Safety Endpoint: Rate of mortality at 30 days

4.2.2 Secondary Endpoints

- Weighted mRS at 180 days
- mRS of ≤ 3 at 180 days
- mRS of ≤ 2 at 180 days
- mRS at 365 days
- Stroke Impact Scale – Mobility at 180 days
- Stroke Impact Scale – ADLs at 180 days
- Stroke Impact Scale – Mobility at 365 days
- Stroke Impact Scale – ADLs at 365 days
- EQ-5D-5L at 180 days
- EQ-5D-5L at 365 days
- Length of hospital stay
- Length of ICU stay
- Length of procedure

4.3 Method of Randomization

Randomization takes place centrally through a commercially available Interactive Web Response System (IWRS). Randomization will occur in a 2:1 ratio to either MIS or MM. The treatment allocation will be balanced by Hemphill Score (0 – 2, 3 – 4) and hemorrhage location (primarily lobar, primarily deep). Once a patient is determined to meet all study eligibility criteria, the Investigator (or authorized team member) obtains the treatment assignment for that subject. Crossover is not permitted after randomization. Once a subject is randomized, the subject is

considered enrolled in the study and that subject must be followed through to the end of study or to subject's termination of consent.

4.4 Blinding

The protocol is designed to have open label treatment assignment. The Penumbra, Inc. clinical team, the Investigator, site study personnel, and the subject will not be blinded to each subject's randomized treatment group throughout the course of the study. Each site will designate one or more individual(s) to perform the blinded mRS assessment at 180 days. The blinded evaluator(s) will be identified on the Delegation of Authority Log and shall not perform data entry or any other tasks that would reveal the study arm assignment of subjects. Due to the nature of the procedure, subjects will be provided with a hat at the 180 day mRS assessment to prevent the blinded assessor from seeing a scar. If the blind is broken for any reason, this will be documented on the case report forms. The blinded evaluator who performs the mRS assessment will be instructed to follow a scripted interview to control for potential bias.

5. Study Population

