6.10.1 Post Discharge Assessments

- Focused Exam, which includes a review of subject's vitals.
- mRS: As described in section 6.4 above. It is preferred that mRS measurements are done at the study site, but if subject is unable to come into the study site for the follow-up visit, a mRS evaluation may be obtained via telephone for 30 day, 90 day, and 365 day using the approved telephone questionnaire/worksheet. The 180 day evaluation of mRS must be conducted in-person.
- Barthel Index: As described in section 6.4 above.
- NIHSS: As described in section 6.4 above.
- GCS: As described in section 6.4 above.

- EQ-5D-5L is a standardized instrument for use as a measure of health outcome. Applicable to a wide range of health conditions and treatments, the questionnaire provides a simple descriptive profile and a single index value for health status. The 90 day EQ-5D-5L should be done using the approved telephone questionnaire if the visit is conducted via the telephone.
- Stroke Impact Scale: Additionally, a quality of life scale outcome measure will be utilized in this study. Quality of life scales are designed to be sensitive to changes in outcome from mild and moderate stroke undetected by other outcome measures. Important parameters not fully interrogated by conventional outcome scales can be assessed by quality of life scales, including emotion, communication, cognition, and social role function. Standard measures, such as the mRS, primarily evaluate physical aspects of stroke outcome, not addressing more relevant quality of life measures. The Stroke Impact Scale is a validated assessment of quality of life specifically in patients with stroke.⁶³

All day 30, day 90, day 180, and day 365 outcome measures will be assessed by a qualified member of the research or clinical team. The schedule of neurological assessments is listed in Table 2. At each visit, the subject medical record will be surveyed for any new or interim neurological adverse or serious adverse events and selected concomitant medication. In addition, the subject, LAR, or approved delegate will be asked about any interim neurological adverse or serious adverse events. The subject, LAR, or approved delegate will also be specifically asked about any interim neurosurgical procedures. Best medical management should be followed throughout the post discharge follow up period.

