6.10.2 Unscheduled Visits

If a subject returns to the study site between follow-up visits a focused exam and mRS value should be obtained and recorded in the unscheduled visit CRF. Subject should also be screened for reportable adverse events and any medications used to treat those events, as well as any changes to medications should be recorded.

Table 2: Schedule of Assessments*

ACTIVITY	INITIAL SCREENING / BASELINE	FINAL SCREENING	TREATMENT PROCEDURE	MM ONLY: 72-HOUR POST RAND (±24 hours)	MIS ONLY: 24-HOUR POST ARTEMIS (±12 hours)	DISCHARGE AND /OR 7 DAYS (± 1 day)	30 DAY (± 14 days)	90 DAY PHONE CALL (± 14 days)	180 DAY (± 21 days)	365 DAY (± 35 days)	UN SCHEDULED
Informed Consent		X									
Verify I/E Criteria		X									
Medical History	X										
Focused Exam		X		X	X	X	X		X	X	X
Standard of Care Labs	X	X ²		X	X	X					
Pregnancy Test⁴		X									
CT/MR	X ¹	X ^{1,2,3}	X	X ¹	X ¹	X ²					
CTA or MRA	X	X ³									
Barthel Index		Historic					X	X	X	X	
NIHSS	X ²	X ⁶		X ⁶	X ⁶	X ⁶	X ⁶	X ^{2, 6}	X ⁶	X ⁶	X ²
GCS	X ²	X		X	X	X	X	X ²	X	X	X ²
mRS⁶		Historic		X	X	X	X	X	X ⁸	X	X
Randomization		X ⁷									
Artemis Procedure⁵			X								
Stroke Impact Scale (QoL)							X		X	X	
EQ-5D-5L QoL							X	X	X	X	
Con Medications	X	X	X	X	X	X	X	X	X	X	X
Adverse Events Review			X	X	X	X	X	X	X	X	X

¹ Image to be sent to central core lab within 14 days of 72-hr post randomization (MM group) or 24-hr post Artemis (MIS group) visit

² If done as standard of care

³ As necessary to demonstrate hemostasis

⁴ For Women of childbearing potential

⁵ Under general anesthesia within 72 hours of ictus if randomized to MIS group

⁶ Performed by certified assessor (or physician) delegated for task

⁷ After all eligibility criteria confirmed

⁸ Performed by blinded certified assessor (or physician) delegated for task

* Subjects in both MM and MIS group should follow medical management per AHA/ESO guidelines

7. Investigator Responsibilities

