10.2. Secondary Efficacy Analysis

The secondary endpoints of Day 180 and Day 365 mRS average improvement in mRS will be analyzed using a generalized linear model. The mRS scores will be weighted as the following: 1.0 for mRS level 0; 0.91 for mRS level 1; 0.76 for mRS level 2; 0.65 for mRS level 3; 0.33 for mRS level 4; 0 for mRS level 5; and 0 for mRS level 6. Statistical analysis of the dichotomized Rankin outcome scores of 0 to 2 and 0 to 3 will be conducted with a logistic regression model. Day 365 mRS analysis will also include ordinal and dichotomous (0 to 2; 0 to 3) outcomes. Group differences will be analyzed for the following: SIS-ADL, SIS-mobility, EQ-5D-5L, length of stay, length of procedure.

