- impute all missing MIS patients as mRS 5/6 and all missing MM patients as mRS 0
- utilize multiple imputation from the longitudinal model to calculate the Bayesian posterior probability of superiority
- estimate 180-day mRS by extending the longitudinal multiple imputation models to include strata for baseline Hemphill Score and hemorrhage location

14. Blinding

The protocol is designed to have open label treatment assignment. The Penumbra, Inc. clinical team, or delegate is responsible for the conduct of the study, the investigator, site study personnel, and the subject will not be blinded to each subject's randomized treatment group throughout the course of the study. The evaluator who performs the 180-day mRS assessment will be blinded to the treatment received by the patient and will be instructed to follow a scripted interview to control for potential bias.

While the CEC review of adverse events specific to the interventional procedure will unblind the members, all members of the CEC will be blinded to the overall primary results of the study.

15. Control of Systematic Error and Bias

Randomization takes place centrally through a commercially available Interactive Web Response System (IWRS). The clinical study will be conducted under a common protocol for each investigational site with the intention of pooling the data for analysis. Every effort will be made to promote consistency in study execution at each investigational site.

The interim analysis of the primary endpoint will be conducted by an independent statistician.

16. Committees

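### A blinded mRS rating is required only at Day 180; none is required for the Day 365 mRS, a secondary endpoint of an open-label trial

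*Protocol*

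**What the plan says.** Treatment is open label. Protocol 4.4 states that "the Investigator, site study personnel, and the subject will not be blinded to each subject's randomized treatment group throughout the course of the study". Against that background the plan protects one rating:

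- Protocol 4.4: "Each site will designate one or more individual(s) to perform the blinded mRS assessment at 180 days". This evaluator may not take on tasks that would disclose the arm, follows a script, and sees the subject wearing a hat that hides any scar. A broken blind is recorded.
- Protocol Table 2, footnote 8: "Performed by blinded certified assessor (or physician) delegated for task". The footnote is attached to the 180 Day mRS cell and not to the 365 Day cell.
- SAP section 14: "The evaluator who performs the 180-day mRS assessment will be blinded to the treatment received by the patient". No other visit is mentioned.

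For Day 365:

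- Protocol 4.2.2 lists "mRS at 365 days" as a secondary endpoint.
- Protocol 6.10.1 says "All day 30, day 90, day 180, and day 365 outcome measures will be assessed by a qualified member of the research or clinical team", with no blinding condition. It also allows remote rating: "a mRS evaluation may be obtained via telephone for 30 day, 90 day, and 365 day using the approved telephone questionnaire/worksheet".
- SAP 10.2 analyzes the weighted score at Day 180 and Day 365, and adds: "Day 365 mRS analysis will also include ordinal and dichotomous (0 to 2; 0 to 3) outcomes". That is three types of analysis, or four analyses if both cut points are counted.

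**The concern.** The mRS depends on the rater's judgement, most of all between adjacent grades. The evaluator, hat, script and record of broken blinds show that the sponsor regards expectation as a real threat to this scale in this trial. The threat is the same at Day 365, but no blinded rating is asked for there.

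At stake is how the one-year result is read. If the difference at Day 365 is larger than at Day 180, or appears only then, part of it could be a change of measurement procedure: blinded and in person at Day 180, possibly unblinded and by telephone at Day 365.

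**Working it through.** **Side by side.** Protocol 4.4, Table 2 footnote 8 and SAP section 14 all limit required blinding to Day 180. They agree with each other, so this is a consistent design choice and not a drafting slip. The point rests on that comparison. The arithmetic below only gives a sense of scale.

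**Step 1: check the tool on the plan's own figure.** The plan states 81% power at a cumulative odds ratio (OR) of 1.7 with a maximum N of 500. Inputs: MM distribution from Protocol Table 3 for mRS 0, 1, 2, 3, 4, 5/6 (3, 10, 7, 7, 14, 59%), 2:1 allocation, final test at one-sided 0.02. Whitehead's proportional-odds formula, with p̄ the pooled category proportions:

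- V = (2/3)(1/3)·N·(1 − Σp̄³)/3 = (2/9)(500)(1 − 0.1339)/3 = 32.08, so √V = 5.664
- Power = Φ(ln 1.7 × 5.664 − 2.054) = Φ(3.005 − 2.054) = 82.9%

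A simulation of the tie-corrected rank test (40,000 runs) gives 81.3%. At one-sided 0.025 the two methods give 85.2% and 83.7%. A fixed N = 500 at 0.02 thus matches the stated 81% closely. The interim rules are in the adaptive design report, which was not available, and are not modelled.

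**Step 2: illustrate rater expectation at Day 365.** The documents give no figure for this, so these inputs are assumptions:

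- no true treatment effect;
- the Day 180 MM distribution holds in both arms at Day 365;
- 5 and 6 are merged as in the primary analysis;
- a share f of living MIS patients is scored one level too well, with no error in the MM arm;
- a share s of the 5/6 group is alive and can be upgraded;
- the threshold is one-sided 0.02, borrowed from the primary endpoint because the documents give none for the Day 365 mRS.

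Worked case, f = 20% and s = 40%. The MIS row becomes:

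- mRS 0: 3 + 0.2×10 = 5.0
- mRS 1: 10 − 2.0 + 1.4 = 9.4
- mRS 2: 7 − 1.4 + 1.4 = 7.0
- mRS 3: 7 − 1.4 + 2.8 = 8.4
- mRS 4: 14 − 2.8 + 0.2×0.4×59 = 15.92
- mRS 5/6: 59 − 4.72 = 54.28

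A proportional-odds fit gives OR 1.191, with ln OR = 0.1748. At N = 500, √V = √[(2/9)(500)(1 − 0.1796)/3] = 5.512. The false-positive rate is Φ(0.1748 × 5.512 − 2.054) = Φ(−1.090) = 13.8%.

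All cases, for f = 5 / 10 / 20%:

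| Share of 5/6 alive (s) | Spurious OR | False-positive rate, N = 500 | False-positive rate, N = 200 |
|---|---|---|---|
| 0% | 1.01 / 1.02 / 1.05 | 2.3 / 2.7 / 3.7% | 2.2 / 2.4 / 2.9% |
| 20% | 1.03 / 1.06 / 1.12 | 2.9 / 4.0 / 7.5% | 2.5 / 3.1 / 4.8% |
| 40% | 1.05 / 1.09 / 1.19 | 3.5 / 5.8 / 13.8% | 2.9 / 4.0 / 7.4% |

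The reference rate without bias is 2%. Only the ordinal analysis is illustrated.

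**The case against.** A reader might infer that the Day 365 mRS is rated by unblinded staff. The documents do not say so. They do not require blinding at Day 365, but nothing forbids a site from using its blinded evaluator. The sentence in Protocol 6.10.1 cannot settle the matter, because it covers Day 180 as well, where the rater is blinded. This objection stands, and the point is confined to what is required.

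A reader might also infer that a claim of lasting benefit rests on this endpoint. The documents make no such claim. SAP 10.4 names eight secondary analyses that may support labeling, and the Day 365 mRS is not one of them. Nor would a Day 365 result be impossible to interpret: a blinded, in-person Day 180 score on the same scale serves as an anchor, deaths need no judgement, and telephone ratings use an approved questionnaire. These objections stand and limit the weight of the point.

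The illustration can fairly be called soft. The upgrade share, the split of 5 and 6, the one-sided bias, the Day 365 distribution and the threshold are all assumed. If no mRS 5 patient is upgraded, or if the trial stops at 200, the effect is small. The table shows this range.

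Finally, concentrating blinding on the primary endpoint is a legitimate choice with no internal contradiction. That is true, but it does not explain why a rater already in place at each site should not also score the same scale at the last visit.

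**Conclusion.** The point holds as a low-cost improvement and not as an error. Blinded mRS rating is required at Day 180 only. The Day 365 mRS, a secondary endpoint with several planned analyses in an open-label trial, has no such requirement and is open to rater expectation.

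The primary analysis at Day 180 and the labeling analyses do not use the Day 365 mRS. Under the stated assumptions the spurious OR runs from about 1.01 to 1.19. The false-positive rate at a borrowed one-sided 0.02 runs from about 2% to 14% at N = 500 and from 2% to 7% at N = 200. These figures show what modest misrating could do; they do not estimate what will happen.

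**What to change.** Amend Protocol 4.4 and 6.10.1, Table 2 (attach footnote 8 to the 365 Day mRS cell) and SAP section 14. The blinded evaluator already designated at each site would then also perform the Day 365 mRS with the same script, either in person with the hat or by the approved telephone questionnaire, and would record any broken blind.

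Cost: no new role, and no change to N, power or alpha. The Day 365 visit also includes adverse event and medication review, which could reveal the arm, so the mRS must be scheduled apart from it. Some raters may already have been unblinded at Day 180. The record of broken blinds would show how often, and a site with more than one blinded evaluator could use another.

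The change should not be extended to the Day 90 mRS with the same rater. Subjects know their arm, and a further contact before Day 180 would give them another chance to disclose it to the person whose primary rating must stay blinded.
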